Women randomized to CSC will receive a telephone counseling call during which the opportunity to complete CRC screening (FOBT or a colonoscopy) and/or mammography will be offered. The CSC will include tailored counseling as well as the ability to schedule BC and CRC screening tests. The combined TIWeb + CSC group will receive a mailed TIWeb followed in four weeks by a CSC with the same opportunity to receive FOBT kits or schedule a colonoscopy and/or mammogram. The nurse counselor, knowing the participant is a good candidate for screening tests, will be trained to schedule CRC or BC screening appointments or to mail FOBT kits to individuals in the intervention groups even if they have not had a recent clinic visit. The usual care group will receive usual care that varies dependent upon the practice setting. Participants will have a baseline telephone or electronic survey prior to randomization that assesses beliefs, knowledge, self-reported CRC & BC screening, and other study variables. Four weeks following intervention, participants will be surveyed via

telephone or electronic survey on CRC & BC beliefs, knowledge, and participant involvement in and satisfaction with the intervention. Again at 6 months, a final telephone or electronic survey will be done and claims data collected. (See Figure 2) A Community Advisory Board will be involved in design and review of interventions, accrual, and intervention delivery.

In order to tell whether or not the two week opt out period is sufficient time for women to opt out, the PI and project manager will monitor a spreadsheet that will be developed for tracking calls made by study staff to women who indicate that they did opt out of the study by returning the refusal postcard, calling the toll free number, or emailing the project manager. If a woman indicates that she did opt out the study staff will apologize and indicate to the project manager or PI that this has happened. The project manager will then make sure her documentation is destroyed. Once this occurrence has happened a total of ten times, the PI will reevaluate the opt out time period and consider revising. Any occurrences will be reported to the IRB at continuing review.

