Barriers to selected CRC screening option	Reduce perceived barriers to colonoscopy, mammography or FOBT	
 • Assess barriers • Counsel on barriers identified 	5
Access	Enhance access to selected CRC & BC screening option	
 • Mail FOBT • Assist with scheduling colonoscopy 	2
Conclude	Summary for patient activation of CRC & BC screening guidelines		

TIWeb program that is narratively rich and applicable to women at all levels of education.

D.7. Cancer Screening Call. (CSC) A computer interface will act as a counseling guide, but nurse counselors will have flexibility in responding to individuals' questions based on the conversation flow. Our team is experienced in training counselors to use these guides without seeming "rote" or "stiff" in presentation. The conversational tone of messages in the program, combined with flexibility of counselors to paraphrase and answer questions, has assured a pleasing presentation. The telephone nurse counselor will call individuals randomized to the CSC alone to schedule the telephone counseling call after they have been consented and baseline data collected. The call will be placed within 1 week of randomization. For individuals who are randomized to the TIWeb+ CSC, the TIWeb will be mailed after randomization and the telephone nurse counselor will call 1 week after this mailing. *The follow up data collection will occur at 4 weeks post intervention.*

Interpersonal communication interventions using telephone counseling have demonstrated

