
D.9. Training for Interviewers and CSC Nurse Counselors. Graduate nurses will be hired and trained as counselors to complete the CSCs. The nurse counselors will have an initial training session consisting of the following elements: 1) project rationale and overview, 2) detailed information about each intervention, 3) delivery practice, 4) a detailed training manual, 5) an extensive question-and-answer period, and 6) breakout for individual training roles and training to use an algorithm developed by [name] to determine eligibility for colonoscopy. Nurse counselors will be trained to appropriately answer spontaneous questions that occur either during telephone interviews or during telephone counseling. Nurse counselors who conduct telephone counseling calls will have all calls recorded. Responding to impromptu questions will be an important part of training so that standardization can be achieved. Role play will be especially important in learning to respond to questions. We will have four hours of role play in which mock participants will challenge nurse counselors with extraneous questions. The nurse counselors for the CSCs will be continuously recorded for quality assurance. The role-playing and taped interviews will be evaluated based on a checklist contained in the **Appendix A**. Initial training will be conducted during a two-day session. The first day will consist of presentations including the following: 1) overview of grant objectives and rationale; 2) detailed demonstration of intervention arms; 3) protection of human subjects and confidentiality issues; and 4) practice in answering impromptu questions.

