*Consistency in intervention delivery is assured through the standardized programming used in the computer-assisted CSC and through taping and review of CSCs. The TIWeb guide the participant through all sections. The CSCs will be continuously recorded for quality assurance. Monthly taping of at least one TIWeb technical assistance session and T1, T2, and T3 interview for each interviewer will allow checks on consistency of performance. Taped interviews and CSC calls will be evaluated based on a checklist contained in **Appendix A**. Research assistants who are not delivering calls as instructed will be given additional training. Research assistants will address any unusual happenings during biweekly meetings. Decisions to modify procedures will be made jointly and documented. The research team will meet monthly to discuss any concerns with implementation of the protocol or collection of interview data. The principal investigators will meet weekly to refine the protocol and training procedures and to discuss ongoing issues.*

Table 6. Measurement of Outcomes: Stage and Adherence for BC and CRC

Stage	CRC Screening Average risk woman	CRC screening At higher risk because of family history	BC Screening
Precontemplation	Is nonadherent to national guidelines and does not intend to have one of the test options in next 6 months	Never had a colonoscopy or had one > 10 years ago and does not intend to have one in next 6 months	Never had a mammogram or had one \geq 15 mo. ago and does not intend to have one in next 6 months
Contemplation	Is nonadherent to national guidelines but intends to have one of the test options in next 6 months	Never had a colonoscopy or had one > 10 years ago and intends to have one in next 6 months	Never had or had mammogram more than 15 months ago but intends to have one in next 6 months
Action (Adherence to any CRC screening)	Had one of the test options since intervention	Had one of the test options since intervention	Had a mammogram since intervention
Action (Adherence to risk appropriate CRC screening)	Had one of the test options since intervention	Had a colonoscopy since intervention	Had a mammogram since intervention

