Group A (nonadherent to CRC but adherent to BC screening guidelines)

Hypothesis 1- Efficacy Analysis: The differences in binary adherence across the four randomized arms will be tested initially with the chi-square test for a 2x4 cross-classification table (adherence by randomized intervention groups). Binary logistic regression analysis, with three dummy variables using usual care as the reference category, will be computed to study the effects of each intervention (TIWeb, CSC, TIWeb +CSC) versus usual care on adherence, while adjusting for any potentially confounding covariates. In addition, model contrasts will be specified to statistically compare each of the three intervention arms to the others. Since the intervention is delivered to the patient and not the provider, analysis of variation in CRC screening by practitioners will be limited. Outcomes of patients who share the same providers may be slightly more correlated than outcomes of patients from different providers. Thus, the within-provider correlation among patients will be assessed with variance components, and if necessary generalized estimating equations (GEE) will be used with logistic regression to account for the within-provider correlation. We will enter as independent variables into logistic models the following: randomized group membership and any demographic covariate (age, race, education, marital status, screening history, baseline stage of adoption, SF12 mental health component, SF12 physical health component) for which the randomized groups differ significantly at baseline using a liberal significance level of 0.20. We will also measure whether subjects report that their physicians have recommended the screening test in the past and the amount of out-of-pocket expense for screening and enter these as covariates. In addition to demographic variables, other potential covariates will be location of TIWeb intervention (use of a computer at home or elsewhere), and whether women in the TIWeb group needed technical help from the research assistant to use the TIWeb program. We plan to include screening history as a covariate in our analysis by using the total number of past screenings for each test since the participant turned 50. For analysis with mammography screening, one covariate will be included (total number of mammograms since age 50). For the analysis of CRC screening, two covariates will be included simultaneously in the models (total number of FOBTs since age 50, and "any previous endoscopic test" [yes/no]). The CRC screening analysis requires two covariates because a history of five FOBTs, for example, is not equivalent to one previous FOBT and one previous colonoscopy or sigmoidoscopy. All variables in the

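### The analysis assesses clustering by physician but not by the counselor who delivers the call, so intervals for call versus no-call contrasts may be too narrow

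*Combined protocol and SAP*

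**What the plan says.** The Hypothesis 1 efficacy analysis in D.13 starts with a four-arm chi-square test and moves to logistic regression with three arm indicators. On correlated outcomes it says: "Since the intervention is delivered to the patient and not the provider, analysis of variation in CRC screening by practitioners will be limited". It then provides: "Thus, the within-provider correlation among patients will be assessed with variance components, and if necessary generalized estimating equations (GEE) will be used". Provider here means the practitioner, and the adjustment is conditional.

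The call is delivered by other people. D.9: "Graduate nurses will be hired and trained as counselors to complete the CSCs". D.1: "Women randomized to CSC will receive a telephone counseling call"; the combined arm also gets the call, while the usual care and TIWeb-only arms get no counseling call. D.7 supplies a computer guide, but "nurse counselors will have flexibility in responding to" questions, and they may paraphrase. Counselors also schedule tests and mail FOBT kits (D.1, D.7).

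Variation between counselors is addressed only through delivery. D.9: "Nurse counselors who conduct telephone counseling calls will have all calls recorded". D.10: "Consistency in intervention delivery is assured through the standardized programming used in the computer-assisted CSC and through taping and review of CSCs". The efficacy analyses in D.13, the power section D.12 and the listed limitations contain no counselor term, ICC or design effect. The number of counselors and the way women are assigned to them are not stated.

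**The concern.** With individual randomization, one physician's patients are expected to fall in all four arms, so a physician effect largely cancels from arm contrasts. A counselor effect does not cancel when a call arm is compared with a no-call arm, because counseling exists on one side only. If some counselors persuade or schedule better than others, women who share a counselor have correlated outcomes and the call arms carry less information than their head count suggests. GEE by physician would not repair this.

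At stake are the width of the intervals for four contrasts (CSC and TIWeb+CSC, each against usual care and TIWeb) and D.12's claim of 80% power for any pair of arms. The wider use of the result matters too: B.8 and the Feasibility/Clinical Relevance paragraph foresee calls made by office staff who are not the trial's counselors.

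**Working it through.** **Inputs from the documents.** D.12: 357 women per arm at 6 months (397 at baseline less 10%). Expected CRC adherence is 20% in usual care, 30% with TIWeb (labeled TIDVD in that table), 40% with CSC and 55% with both. Stated power is 0.87 (usual care v TIWeb), 0.80 (TIWeb v CSC), 0.98 (CSC v both) and 0.99 for the other three pairs.

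**Assumptions.** Two-sided 5% test (no efficacy alpha is stated; D.13 reports 95% intervals). Number of counselors k = 4 to 10. Counselor ICC = 0 to 0.02. Women are shared evenly among counselors, and counselors are a sample from a wider pool.

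**Step 1: reproduce the plan's power.** For TIWeb v CSC with independent outcomes:
- SE under the null = √(2 × 0.35 × 0.65 / 357) = 0.0357
- SE under the alternative = √((0.21 + 0.24) / 357) = 0.0355
- power = Φ((0.10 − 1.96 × 0.0357) / 0.0355) = Φ(0.846) = 0.80

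The same formula gives 0.871 for usual care v TIWeb, 0.981 for CSC v both, and above 0.99 for the rest. The stated figures therefore assume full independence.

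**Step 2: add counselor clustering in the call arm only.**
- Design effect in a call arm: DE = 1 + (357/k − 1) × ICC
- Type I error of the unadjusted test: 2 × (1 − Φ(1.96 / √((1 + DE)/2)))
- TIWeb v CSC power after allowing for clustering: Φ((0.10 − 1.96 × SE0) / SE1), with SE0 = √(0.2275 × (1 + DE) / 357) and SE1 = √((0.21 + 0.24 × DE) / 357)

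| k | ICC | DE | Type I error | TIWeb v CSC power |
|---|---|---|---|---|
| any | 0 | 1.000 | 5.0% | 0.80 |
| 10 | 0.005 | 1.173 | 6.0% | 0.77 |
| 8 | 0.005 | 1.218 | 6.3% | 0.76 |
| 10 | 0.01 | 1.347 | 7.0% | 0.73 |
| 6 | 0.01 | 1.585 | 8.5% | 0.69 |
| 4 | 0.01 | 1.883 | 10.3% | 0.65 |
| 10 | 0.02 | 1.694 | 9.1% | 0.67 |
| 6 | 0.02 | 2.170 | 12.0% | 0.60 |
| 4 | 0.02 | 2.765 | 15.3% | 0.53 |

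Last row in full: DE = 1 + 88.25 × 0.02 = 2.765. Type I error = 2 × (1 − Φ(1.96/1.372)) = 15.3%. Power = Φ((0.10 − 1.96 × 0.0490)/0.0495) = Φ(0.08) = 0.53. A beta-binomial simulation with 20,000 runs per setting gave 15.1% to 15.3% type I error for this row.

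**Step 3: small-sample degrees of freedom.** Let v_c = DE × 0.24/357 and v_n = 0.21/357. Satterthwaite df = (v_c + v_n)² / (v_c²/(k − 1) + v_n²/356). With a t critical value on these df, TIWeb v CSC power is about 0.72 (k = 8, ICC 0.005, df about 20), 0.62 (k = 6, ICC 0.01, df about 12) and 0.38 (k = 4, ICC 0.02, df about 5).

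**Step 4: the other contrasts.** In the worst row (k = 4, ICC 0.02), with the normal critical value, power is 0.99 for CSC v usual care and above 0.99 for TIWeb+CSC against usual care or TIWeb. With Satterthwaite df, using each pair's own variances, these become about 0.90, above 0.99 and 0.98. TIWeb v usual care involves no counselor. TIWeb+CSC v CSC kept a simulated type I error of about 5% when the same counselors served both arms evenly.

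**The case against.** A reader might infer that the error bars **are** too narrow and that the tests **do** reject too often. The documents do not support that. Both statements need an ICC above zero, and none is given. The computer guide, role play, recording of every call, checklist review and retraining all push the ICC down. That stands, and it is why the range starts at zero. These measures do not show that the ICC is zero, however, and the plan does not estimate it.

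The inflation also depends on the target of inference. If the question is the effect with these counselors, and women are assigned to them without selection, the ordinary standard error is adequate. In a simulation with counselors who differ but whose average effect is zero, the unadjusted test rejected about 5% of the time. The hypotheses are worded as differences among randomized women, so this reading is open. The random-counselor view is a choice, supported by the wider use foreseen in B.8 and under Feasibility/Clinical Relevance.

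Three further points stand. The lower power figures describe a corrected analysis, not the unadjusted test as planned. The no-call arms may not be wholly free of nurse contact: D.1 lets the nurse counselor schedule tests or mail kits for women in the intervention groups, and TIWeb women have a number to call. Finally, under intention to treat some women in the call arms will never be reached and so share no counselor; 357/k then overstates the cluster size by an unknown amount.

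It would also be too generous to say that the plan handles physician clustering, since GEE is used only if judged necessary.

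**Conclusion.** The omission is certain; its size is not. The plan assesses correlation at a level that should matter little for arm contrasts and is silent on the level that sits inside the two call arms. If counselors differ and the result is meant to reach beyond them, call versus no-call intervals may be too narrow, with consequences between nil and those in the last row of the table. That range rests wholly on the assumed counselor numbers and ICCs.

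The practical exposure is TIWeb versus CSC, the only call versus no-call pair planned at the 80% floor. The documents do not support a claim that the trial's main comparisons with usual care are in danger of losing power. This calls for an inexpensive addition to the plan, not a redesign.

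**What to change.** 1. Record the ID of whoever delivers each call. State how many callers there are and how women are assigned to them.
2. Reconcile who makes the call. Item 6 of the D.4 summary and part of D.9 assign it to research assistants; D.7 and the rest of D.9 assign it to nurse counselors.
3. In D.13, pre-specify a sensitivity analysis for every call versus no-call contrast: a partially nested logistic model with a counselor random effect active only in the CSC and TIWeb+CSC arms, small-sample degrees of freedom, and the estimated counselor ICC reported.
4. Where practical, have the same counselors serve both call arms without selective assignment, so that TIWeb+CSC versus CSC stays clean.

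Items 1 to 3 cost one data field and some wording. Calls are already recorded, staff keep activity logs, and counseling time is tracked per participant, so the ID should be easy to capture if this is done prospectively. Item 4 affects operations and may not be fully achievable. The statistical price is wider intervals in the sensitivity analysis and an imprecise variance component when counselors are few. For that reason I would not require this model as the main analysis.

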D.12. Sample Size and Power Analysis: The *primary efficacy hypothesis in this area of research is adherence to screening. Therefore, adherence to CRC and BC screening at 6 months has driven our choice of sample size.* Originally, we proposed conducting analysis with two separate groups based on initial mammography status: 1) women who were adherent to mammography but not to colorectal cancer (CRC) screening, and 2) women who were adherent to neither mammography nor CRC screening. By testing these groups separately, we required a sample size of 2616 to achieve 80% power between both the control and intervention groups and between any combinations of groups. In re-considering this approach, we realized that since the outcome of CRC screening was common across both groups A and B, this was not the most efficient design to test our outcomes. We are proposing analyses using one group of women, all of whom will be non-adherent to CRC screening at baseline. In this group, some women will be adherent to mammography guidelines (i.e., had a mammogram in the past 15 months) and others will be non adherent. For Aim 1, when we examine intervention effects on the outcome of CRC screening, we will control for baseline adherence to mammography. For Aim 2, we will use only the sub-group of women who were not adherent to either breast or CRC screening at baseline. Using this approach will reduce the sample size needed and reduce the overall costs of the study, more closely aligning the budget with the amount awarded. Most importantly, revising our analytical approach will enable us to achieve our initial Aims despite the reduced sample size.

Specifically, for the outcome of CRC screening adherence, we had justified sample size in the original proposal to achieve 80% power to detect differences between intervention groups, *separately* for two groups of women depending on their baseline breast cancer screening adherence status.

Group A includes women who were nonadherent to CRC screening but adherent to BC screening, and **Group B** includes women nonadherent to both CRC and BC screening.

We realize now that it is unnecessary to perform the analysis of CRC adherence separately for the two groups (A and B). Instead the Group variable (A vs B) can be entered in the model using baseline mammography screening as a covariate.

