Thus, the hypotheses for Aim 1 can now be conceptualized as

Aim 1:

Hypothesis 1 (Primary outcome): There will be differences in CRC screening adherence and stage of adoption, when controlling for adherence to BC screening at baseline, among women who are randomized to 1) usual care; 2) a TIDVD; 3) a CSC, and 4) a TIDVD plus a CSC.

Aim 2:

Hypothesis 2 (Secondary outcome): In the group that is nonadherent to both CRC and BC screening at baseline, there will be differences in adherence to both CRC and BC screening and stage of adoption, among women who are randomized to 1) usual care; 2) a TIDVD; 3) a CSC, and 4) a TIDVD plus a CSC.

D.13. Analyses. Descriptive statistics will be computed for all variables, using stem-and-leaf plots, central tendency indices, variability indices, and frequency distributions. We will compare demographic information at baseline across the four randomized groups (usual care, TIWeb, CSC, and TIWeb + CSC), using the analysis of variance (ANOVA) for continuous variables (describing with means and standard deviations) and using the Pearson chi-square test for categorical variables (describing with cross-classification tables). If the ANOVA parametric assumptions of normality and equal variances are not met, we will perform the nonparametric Kruskal-Wallis test for the continuous variables. If there are significant baseline differences between the two intervention groups at a liberal significance level of 0.20, we will adjust for those characteristics in subsequent logistic regression analyses.

Aim 1: Analysis for intervention efficacy: Women in **Group A women** are nonadherent to CRC screening but adherent to BC screening at baseline and thus could become adherent to *CRC screening*. *Depending on whether a woman is at increased risk (due to family history) or average risk, we will code each participant as risk-appropriate adherence or adherence to any CRC screening. For women at average risk, these categories will be identical. For women at high risk, completion of a colonoscopy is needed to classify them as adherent to the risk-appropriate test. Thus, two outcomes will be tested in relation to CRC adherence: 1) adherence to any CRC test; and 2) adherence to a risk-appropriate test. Women in Group B will be nonadherent to both CRC and BC screening at baseline and thus could remain nonadherent to both, become adherent to one, or become adherent to both screenings.*

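### Seven baseline covariates enter the efficacy logistic model only if the arms differ at p<0.20; the covariate list should be fixed in advance

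*Combined protocol and SAP*

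**What the plan says.** **The gated covariates.** D.13 (Hypothesis 1, Efficacy Analysis) puts arm into the logistic model and adds a candidate variable only if it is one "for which the randomized groups differ significantly at baseline using a liberal significance level of 0.20". The candidates for this test are listed as "age, race, education, marital status, screening history, baseline stage of adoption, SF12 mental health component, SF12 physical health component". The opening paragraph of D.13 gives the rule in general form: "If there are significant baseline differences between the two intervention groups at a liberal significance level of 0.20, we will adjust for those characteristics". It refers to two groups, although the same paragraph names four randomized arms.

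**The covariates not gated.**
- Baseline mammography adherence (Group A or B). D.12 says of Aim 1 that "when we examine intervention effects on the outcome of CRC screening, we will control for baseline adherence to mammography", and Hypothesis 1 in Specific Aims and in D.12 repeats this. D.12 also puts it more loosely: "Instead the Group variable (A vs B) can be entered in the model using baseline mammography screening as a covariate".
- CRC screening history. D.13 says "For the analysis of CRC screening, two covariates will be included simultaneously in the models", namely the number of FOBTs since age 50 and any previous endoscopic test.
- Past physician recommendation and cost. D.13 will measure the recommendation and "the amount of out-of-pocket expense for screening and enter these as covariates".

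**Where the text disagrees.** Screening history is in the gated list and is also included unconditionally in the same paragraph. The D.13 model list does not name Group A/B, and the Hypothesis 1 analysis still stands under a Group A heading. D.12 has by then merged the two groups for the CRC outcome.

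**Post-randomization variables.** D.13 also lists as potential covariates where the TIWeb was used and whether technical help was needed. D.9 adds help contacts to the final analysis as a covariate.

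**The concern.** When arms are randomized, the null hypothesis of a baseline balance test is true by design. A p<0.20 screen therefore admits a variable about one time in five, however strongly it predicts screening. A covariate earns its place by its relation to the outcome, and the plan itself treats several gated variables as related to it. Section B.9 ties age, education and marital status to both screenings. Table 6 separates the two baseline stages by whether the woman intends to be tested in the next 6 months, which is about the window of the primary outcome.

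Two things are at stake. First, some precision that the baseline data could supply is usually left unused. Second, D.13 promises adjusted odds ratios. The value of an odds ratio changes with the covariates conditioned on, even with perfect balance, so under this rule chance imbalance decides which quantity is reported.

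**Working it through.** **1. The plan's own power.** Inputs from the D.12 table: 6-month adherence of 20%, 30%, 40% and 55%, with 357 per arm. Alpha is not stated; two-sided 0.05 is assumed. The tightest contrast is arm 2 (web program, labelled TIDVD in the table) against arm 3 (CSC), with the pooled-variance formula:
- SE under the null = √(2 × 0.35 × 0.65 / 357) = 0.0357
- SE under the alternative = √((0.30 × 0.70 + 0.40 × 0.60) / 357) = 0.0355
- Power = Φ((0.10 − 1.96 × 0.0357) / 0.0355) = 0.801, against .80 in the table

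The others also reproduce: 1v2 0.871, 3v4 0.981, the rest above 0.999. The table uses no covariates, and 2v3 sits at its 80% target.

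**2. How often the rule acts.** Each gated variable enters with probability 0.20 (0.193 to 0.216 in simulation). For the seven that are gated without contradiction, assumed independent:
- expected number entering = 7 × 0.20 = 1.4
- P(at least one) = 1 − 0.8⁷ = 0.79
- P(a given one is left out) = 0.80

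Counting screening history as an eighth gives 8 × 0.20 = 1.6 and 1 − 0.8⁸ = 0.83.

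**3. Power forgone on 2v3.** The documents give no covariate–outcome strength, so every odds ratio (OR) below is an assumption. Logistic Wald tests, 357 per arm, the plan's marginal rates, 4,000 simulated trials per row (Monte Carlo SE about 0.006).

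Stage split 50/50, Group A/B 107/250 per arm; the last column adjusts for stage and Group A/B:

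| Stage OR | Unadjusted | p<0.20 rule | Prespecified |
|---|---|---|---|
| 2 | 0.81 | 0.81 | 0.82 |
| 3 | 0.80 | 0.80 | 0.82 |
| 4 | 0.81 | 0.82 | 0.85 |

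This credits the fix with Group A/B, which D.12 already promises. With Group A/B in both models and only stage gated (2,500 trials, Group OR assumed 1 to 2), the gain is 0.6–0.9 points at stage OR 2, 1.6–2.4 at OR 3 and 2.1–3.2 at OR 4.

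One continuous covariate and no others in the model:

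| OR per SD | Unadjusted | p<0.20 rule | Prespecified | Gain over rule |
|---|---|---|---|---|
| 1.5 | 0.813 | 0.820 | 0.829 | 0.9 points |
| 2.0 | 0.803 | 0.810 | 0.837 | 2.7 points |
| 2.5 | 0.799 | 0.815 | 0.860 | 4.5 points |
| 3.0 | 0.812 | 0.831 | 0.882 | 5.1 points |

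**4. Type I error.** With all arms at 30% and OR per SD of 2.0 or 3.0, the rule rejected in about 0.045 to 0.051 of trials.

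**5. Which odds ratio.** For 30% against 40%, the unadjusted OR is (0.40/0.60) / (0.30/0.70) = 1.56. With stage split 50/50 and stage OR k, the odds x in the lower stage solve x/(1+x) + kx/(1+kx) = 2p:
- k = 2: x = 0.296 at p = 0.30 and 0.466 at p = 0.40, so the stage-adjusted OR is 1.57
- k = 4: x = 0.194 and 0.317, so it is 1.63

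The shift is small, but under the rule it appears or not by chance.

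**The case against.** **The rule does some good and is not discretionary.** It names its candidates and threshold and uses no outcome data. It also adjusts when a prognostic variable happens to be unbalanced, which is why its simulated power is at or slightly above the unadjusted figure. The first efficacy test is a fixed, unadjusted chi-square. All of this stands, so it would be too strong to say that the whole primary analysis is unknown until the data are seen; only the adjusted model is. A prespecified adjustment covers the unbalanced case too, and does so every time.

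**Much is already outside the gate.** A reader might infer that no covariate enters without a significant imbalance, and that the precision from screening history and the enrolment stratum is lost. The documents do not support this. Group A/B is committed in D.12 and Hypothesis 1. The two CRC-history terms, physician recommendation and cost enter in D.13 without a test. With these in the model, the further loss from gating the rest is probably at the low end of the range.

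**The Group A/B omission may be only a leftover.** Under a Group A heading that variable is constant, so the list need not name it. That is a fair reading, but a programmer working from D.13 alone would fit the model without it.

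**Stage as the strongest predictor.** A reader might infer this from Table 6. No section ranks the covariates or gives an odds ratio for stage. Its definition makes it a likely strong predictor and no more.

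**Conclusion.** The point holds for seven variables: age, race, education, marital status, baseline stage and the two SF-12 scores. They are admitted on chance imbalance, each is left out about 80% of the time, and the reported adjusted odds ratio depends on that chance. The loss is modest: about 1 to 3 points of 2v3 power for assumed stage odds ratios of 2 to 4, and up to about 5 points if a single covariate is as strong as an assumed OR of 3 per SD. The 79% and 1.4 figures assume independence.

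A reader might go further and conclude that the rule inflates type I error or undercuts the stated power. Neither follows. Simulated type I error stayed near 0.05. The table's power rests on unadjusted proportions, and the rule does not take power below them. That 2v3 has no slack makes the forgone gain worth having but does not show harm. The contradiction on screening history and the missing Group A/B term need reconciling in any case.

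**What to change.** - Delete the p<0.20 rule from both places in D.13.
- Prespecify one primary logistic model for CRC adherence: arm, Group A/B (randomization is within it, per D.1), baseline stage of adoption, number of prior FOBTs, any prior endoscopic test, and a fixed set of demographics, for example age, race, education and marital status.
- Use only values recorded before randomization. If physician recommendation and out-of-pocket cost are kept, take their baseline values.
- Exclude TIWeb location and technical-help contact (D.9, D.13) from the efficacy model. They arise after randomization and only in the TIWeb arms.
- Reconcile the two statements on screening history, name Group A/B in the D.13 list, replace the Group A heading, and correct the reference to two intervention groups.
- Keep the unadjusted chi-square and report it beside the adjusted result.

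The cost is analysis-plan wording: no new data and no change to the sample size.
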